### 1. SYNOPSIS

Study Title	SleepSure: a randomised controlled trial to assess the effects of eye masks and earplugs on the quality of sleep for patients in hospital.			
Internal ref. no. / short title	SleepSure: a study aimed at improving sleep for hospital inpatients			
Study Design	Randomised Controlled Trial			
Study Participants	Patients admitted to adult general medical and surgical wards at Oxford University Hospitals NHS Foundation Trust			
Planned Sample Size	400			
Planned Study Period	01 February 2016- 31 January 2017 Pilot data collection 01 February 2016 to 14 February 2015 Recruitment 01 March 2016 – 31 May 2016 (last follow-up 14 June 2016)			
	Objectives	Outcome Measures		
Primary	Do earplugs and eye masks help hospital patients to sleep better?	SleepSure Questionnaire, based on the validated Richards-Campbell Sleep Questionnaire		
Secondary	Does the use of earplugs and eye masks lead to a reduced length of stay, reduced incidence of falls or reduced use of sleep aid medication? How many patients provided with earplugs and an eye mask choose to use them?	Length of stay (days) Number of falls recorded during stay Doses of zopiclone (sleeping tablet) used to help sleep during stay Use of earplugs and eye masks (SleepSure sleep questionnaire)		

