### 4. OBJECTIVES AND OUTCOME MEASURES

Objectives	Outcome Measures	Timepoint(s) of evaluation of this outcome measure (if applicable)
Primary Objective Do ear plugs and eyemasks improve inpatient experience of sleep?	SleepSure sleep questionnaire	Questionnaire given >1 day after recruitment
Secondary Objectives A) How many patients provided with eye masks and earplugs choose to use them?	SleepSure sleep questionnaire	Questionnaire given >1 day after recruitment
B) Does the use of earplugs and eye masks lead to reduced length of stay?	Length of stay data from hospital administration system	After discharge
C) Does the use of earplugs and eye masks lead to reduced use of sleep aid medication?	Drug chart data from electronic records.	After discharge
D) Does the use of earplugs and eye masks lead to a reduced incidence of falls?	Falls data from centrally collated routinely collected information	After discharge

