# **10.1.** Description of Statistical Methods

There will be no interim analysis.

The primary analyses will be to compare the two groups on all items collected, using t-test and Mann-Whitney U tests as appropriate with two-tailed testing (i.e. accepting that harm is also possible). The expectation is that the intervention group will have:

- Better sleep on the questionnaire
- Less use of night sedation over their hospital stay
- Less falls over their hospital stay
- A shorter length of stay

Secondary analyses will investigate:

- Variation between wards on all measures, irrespective of patient group.
- Reported use of and problems with the earplugs and eye masks.

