## 10.2. The Number of Participants

There is no data to allow sample size calculation, nor are there data on recruitment and loss of patients. We estimate that it should be possible to recruit a total of 400 patients, which should be sufficient to detect any worthwhile benefit.

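### The primary outcome is a whole questionnaire with no defined sleep score, and the primary analysis as worded allows each sleep item its own test

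*Combined protocol and SAP*

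**What the plan says.** The synopsis (section 1) lists the primary outcome measure as "SleepSure Questionnaire, based on the validated Richards-Campbell Sleep Questionnaire". Section 4 asks "Do ear plugs and eyemasks improve inpatient experience of sleep" and enters only the questionnaire as the measure, given once, more than a day after recruitment. Secondary objective A, "How many patients provided with eye masks and earplugs choose to use them", is read from the same form at the same time.

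Section 10.1 states: "The primary analyses will be to compare the two groups on all items collected, using t-test and Mann-Whitney U tests as appropriate". Testing is two-tailed. The sleep result that the plan expects is "Better sleep on the questionnaire". Reported use of the aids, and problems with them, are listed there under secondary analyses.

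No section lists the sleep items, their response scale, a total or mean score, which direction is better, how a partly completed form is handled, a significance level or a multiplicity rule. The table of contents shows no scoring section or appendix. Section 10.3 excludes patients who did not complete the questionnaire, but does not say whether one blank item makes a form incomplete.

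**The concern.** A questionnaire is an instrument, not an outcome variable. Until the plan says which number per patient answers the primary question, the answer is open in two ways. If the sleep items disagree, nothing in the plan says whether the trial succeeded. If one item reaches nominal significance and the others do not, nothing stops that item being reported as better sleep.

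The setting makes this matter more. Patients know whether they were given the aids. Section 13.7 acknowledges expectation bias and decides to offer controls nothing. Section 7.5 provides no baseline sleep measure. The primary conclusion therefore rests on one unblinded self-report after randomisation, so its definition needs to be fixed in advance. It also bears on sample size: section 10.2 offers no calculation, and none can be made until the outcome is one defined variable.

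**Working it through.** **The plan's own figure.** The only figure is the total of 400. It cannot be reproduced, because section 10.2 says no data exist for a calculation and gives no effect size, standard deviation (SD), power or significance level.

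**Inputs**
- From the documents: 400 patients with equal allocation in expectation, so about 200 per arm; two-tailed testing.
- Assumed, because the documents are silent: 3 to 8 sleep items (k), a common correlation r of 0.3 to 0.9 between the item test statistics, 5% two-sided per item, 80% power and no loss of patients.

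**Step 1: chance of at least one false-positive sleep item when the aids have no effect.** For independent items the chance is 1 − 0.95^k in either direction and 1 − 0.975^k in favour of the aids. For k = 5 these are 1 − 0.95^5 = 22.6% and 1 − 0.975^5 = 11.9%. Correlated items were simulated as Z_j = √r·S + √(1 − r)·E_j, with S and E_j standard normal, 400,000 draws and a threshold of 1.96. Each cell gives either direction / favouring the aids:

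| Items | r = 0.3 | r = 0.5 | r = 0.7 | r = 0.9 |
|---|---|---|---|---|
| 3 | 13.6% / 6.8% | 12.5% / 6.3% | 10.9% / 5.4% | 8.4% / 4.2% |
| 5 | 21.0% / 10.5% | 18.3% / 9.2% | 14.8% / 7.4% | 10.1% / 5.0% |
| 8 | 30.0% / 15.1% | 25.0% / 12.5% | 19.1% / 9.5% | 11.9% / 5.9% |

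One pre-specified score gives 5% / 2.5%. A free choice between t-test and Mann-Whitney for each item adds flexibility that these figures do not count.

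**Step 2: detectable difference.** In units of the SD of the variable tested, it is (z for alpha + z for power) × √(2/n). One score at 5%: (1.960 + 0.842) × √(2/200) = 0.28 SD. Five items with Bonferroni (1% each): (2.576 + 0.842) × √(2/200) = 0.34 SD per item. At a true difference of 0.28 SD, the power of one test falls from 80% to 59%.

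**Step 3: when a mean score helps and when it hurts.** The variance of a mean of k items relative to one item is (1 + (k − 1)r)/k. For k = 5 and r = 0.5 this is (1 + 4 × 0.5)/5 = 0.60, so the SD ratio is √0.60 = 0.775. An effect shared by all items is therefore easier to detect on the mean. An effect on one item only is diluted: 0.4 SD on one of five items moves the mean by 0.4/5 = 0.08, which is 0.08/0.775 = 0.10 of the score's SD. With 200 per arm, power is about 98% on the affected item and about 18% on the mean.

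**The case against.** The strongest objection concerns the word for what is compared in section 10.1. It may mean data items rather than questionnaire items. Section 7.6 lists the data to be recorded: stay, falls, zopiclone doses and, as one entry, the questionnaire results. Section 10.1 then gives four expectations, of which sleep is one. On that reading there is a single sleep comparison and the inflation in step 1 does not arise. This stands as a possible reading, so item-level testing is something the text allows, not something it establishes. It does not rescue the definition: the single sleep comparison would still have no score, direction or named test.

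Several stronger inferences are tempting, and the documents do not support them.
- A reader might infer that the sponsor means to pick a favourable item. Nothing shows this.
- A reader might infer that having aid-use items on the same form feeds the better-sleep claim. It cannot: aid use is a separate secondary outcome for patients given the aids, and section 10.1 analyses use and problems as secondary. Those items show only that the form as a whole cannot serve as the sleep score.
- A reader might infer that the adapted form is invalid. The synopsis applies the word validated to the parent instrument. The documents neither claim nor deny validation of the adaptation.

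A further objection is that a mean score can hide a real effect. Section 3 names noise and light as causes of poor sleep, so an effect concentrated in some items is plausible. Step 3 shows that this cost could be large.

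**Conclusion.** The point holds. The primary sleep outcome has no defined score, and the primary analysis as worded leaves room for several primary sleep tests with no rule for deciding between them. Under the stated assumptions, the false-positive chance for the primary question is 8% to 30% in either direction and 4% to 15% in favour of the aids, against 5% and 2.5% for one score. With 5 items correlated 0.5 it is 18% and 9.2%. The favourable-direction figures are the ones that bear on a claim of better sleep.

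These sizes are illustrative. The questionnaire is not in the documents, so the number of items, their correlation and any scoring printed on the form are unknown, and no significance level is stated. The finding that the score is undefined does not depend on them, and it holds on either reading of section 10.1. It should be corrected, and it can be corrected fully in advance.

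**What to change.** In sections 1, 4 and 10.1, before any outcome data are seen by arm (pilot data included):

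- Define the primary outcome as one score per patient: the unweighted mean of the questionnaire's sleep-rating items, listed by name, on a common scale with the better direction stated.
- State the missing-item rule (how many items must be answered for a score to be computed) and align section 10.3 with it.
- Name one test for the primary comparison at a two-sided 5% level, and rest the primary conclusion on that result alone.
- Report individual sleep items as secondary or descriptive. Keep aid use and problems as the secondary outcomes they already are, outside the score.

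The cost is protocol wording only: the sponsor holds the form and no new data are needed. Section 5 pools the pilot (up to 20 of the 400 patients) only if the protocol is not changed. The amendment is therefore best made before the pilot, or should say that it leaves data collection unchanged. The statistical cost is lower power for an effect confined to one aspect of sleep, which would then be reported as a secondary finding. If the sponsor expects such an effect, that aspect can be named as the primary outcome instead, on the same condition that it is fixed in advance.

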# 2. ABBREVIATIONS

CI	Chief Investigator
CRF	Case Report Form
GCP	Good Clinical Practice
GP	General Practitioner
ICF	Informed Consent Form
NHS	National Health Service
NRES	National Research Ethics Service
Ы	Principal Investigator
PIL	Participant/ Patient Information Leaflet
R&D	NHS Trust R&D Department
REC	Research Ethics Committee
SOP	Standard Operating Procedure

Clinical Research Protocol Template version 10.0

CONFIDENTIAL © Copyright: The University of Oxford and Oxford University Hospitals NHS Foundation Trust 2015 Page 4 of 15

## 3. BACKGROUND AND RATIONALE

#### **Background**

Patients consistently complain of lack of sleep due to noises throughout the night from: patients, staff, machines and buzzers as well as complaining about bright lights being left on, monitors left active and LEDs flashing throughout the night. This has a severe negative impact on a patient's hospital experience, and has been associated with increased risk of acute confusion, increased medication usage with their side-effects, delayed hospital discharge (at a cost of £273 per day) and worse health outcomes. In this project we aim to investigate whether the simple solution of earplugs and an eye mask can improve the inpatient experience through enhancing sleep.

#### The question

Our question is simple: Does the provision of earplugs and eye masks improve the sleep of hospital inpatients?

Secondary questions are whether this provision leads to a reduced length of stay, reduced incidence of falls and reduced use of sleep aid medication. We also wish to discover how many patients provided with earplugs and an eye mask choose to use them.

#### The evidence

Whilst use of earplugs and eye masks has a limited evidence base as a sleep adjunct in general hospital wards, there have been a number of small scale randomised trials in the intensive care unit setting where their use has been associated with:

- 1) An objective improvement in night time  $sleep^{(9,10)}$
- 2) A subjective enhancement of patient experience
- 3) A significant reduction and delayed incidence of acute confusion
- 4) A reduction in the use of morphine

#### The population

The population studied will be individuals admitted to Oxford University Hospitals NHS Foundation Trust during the study period onto any ward admitting eligible patients for at least one night. The precise inclusion and exclusion criteria will be defined more specifically later in the protocol.

#### Risks to participants

1) Allergies: Risk of patient or staff having an allergic reaction to the product.

Likelihood: 1/5 Remote Severity: 4/5 Severe Total risk score: 4/25 low risk Mitigate risk by choosing earplugs and eye masks made from hypoallergenic materials, manufactured in quality plant approved with the CE mark. Earplugs and eye masks themselves or the literature provided with them will describe their composition/materials and they will only be provided to patients with the mental capacity to use them safely in an informed manner (similar to use on an aircraft).

- Swallow/Choking risk: Risk of patients swallowing, breathing in and/or choking on earplugs. Likelihood: 1/5 Unlikely Severity: 4/5 Moderate risk Total risk score: 4/25 low risk Mitigate risk by restricting earplugs and eye masks to patient over 18 years old with capacity and awareness/ability to learning from information leaflets of how to use ear plugs/eye masks.
- 3) Infection risk: Risk of spreading infections from one patient to another and of increasing risk of patients getting otitis externa (outer ear infections). Likelihood: 3/5 Possible
   Severity: 2/5 minor
   Total risk score: 6/25 Low risk
   Mitigate risk by advising patients with ear infections not to use earplugs. Have earplugs and eye masks as single patient use (for disposal on discharge) and replace earplugs and eye masks if soiled or contaminated.
- Pressure sores: Risk of earplugs and eye masks causing a pressure ulcer if left in the bed. Likelihood: 1/5 Remote Severity: 3/5 moderate Total risk score: 3/25 Low risk Mitigate risks by good nursing practice of checking the bed for anything lost on top of the mattress, making the bed daily and frequently turning patients with high risk of pressure ulcers, as well as pressure reducing mattresses and pressure removal from damaged sites.
- 5) Increased confusion/risk of falls: increased confusion as patients forget to remove ear plugs and or eye masks and attempt to walk with ear plugs/eye masks still in place. NB/There is no evidence that this occurs, but it is conceivable that it could. Likelihood: 2/5 unlikely Severity: 3/5 moderate Total risk score: 6/25 Low risk Mitigate risk by never applying earplugs and eye masks to a patient without their express and informed request. Removing/not supplying ear plugs/eye masks to confused/confused patients who do not have mental capacity to use the aids.
- 6) Missing alarms: risk of missing light and sound from fire alarms

  Likelihood: 2/5 Possible
  Severity: 2/5 Minor
  Total risk score: 4/25 Low risk
  Mitigate risk by ensuring nursing/healthcare staff wake and inform patients of fire alarm and
  mobilise them to the appointed safe place as is the routine fire protocol. Most patients are

mobilise them to the appointed safe place as is the routine fire protocol. Most patients are dependent upon healthcare staff to mobilise them regardless of their awareness of fire alarms. Most patients are also unable to distinguish between the differing alarms in hospital and are dependent upon staff for that information.

### 4. OBJECTIVES AND OUTCOME MEASURES

Objectives	Outcome Measures	Timepoint(s) of evaluation of this outcome measure (if applicable)
Primary Objective Do ear plugs and eyemasks improve inpatient experience of sleep?	SleepSure sleep questionnaire	Questionnaire given >1 day after recruitment
Secondary Objectives A) How many patients provided with eye masks and earplugs choose to use them?	SleepSure sleep questionnaire	Questionnaire given >1 day after recruitment
B) Does the use of earplugs and eye masks lead to reduced length of stay?	Length of stay data from hospital administration system	After discharge
C) Does the use of earplugs and eye masks lead to reduced use of sleep aid medication?	Drug chart data from electronic records.	After discharge
D) Does the use of earplugs and eye masks lead to a reduced incidence of falls?	Falls data from centrally collated routinely collected information	After discharge

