# 5. STUDY DESIGN

#### Randomised controlled trial

Pilot data collection 2 weeks from approval of study. 3 months data proper once pilot data has been reviewed and any required changes noted. Data collected from adult inpatients on 10 inpatient wards. Pilot data collection is to identify any problems with the data collection that may arise. If no changes to the protocol are made then this pilot data will be incorporated with the data proper.

Targeted recruitment population: 400 patients total including up to 20 from pilot data. Patients randomised to either intervention (earplugs and eye masks) or control (routine care).

Intervention will be allocated via pre-performed simple randomisation concealed in opaque envelopes with intervention and non-intervention envelopes indistinguishable from one another which will be distributed in batches to each ward engaged in the study.

SleepSure sleep questionnaire will be given to all patients >1 day after recruitment.

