### 6.2 Inclusion criteria:

Eligible candidates at the point of enrolment must:

- Be 18 years of age
- Be expected to stay in Oxford University Hospitals NHS Foundation Trust for at least one more night
- Be able to understand and use earplugs and eye mask.
- Have basic understanding of English reading and writing.
- Be considered likely to have the Mental Capacity to give consent for use of personal data in the study at the point of filling in the SleepSure Questionnaire (>1 day after recruitment). NB/ Data will not be collected from individuals who are unable to give consent with the filling in of the SleepSure questionnaire.
- Be expected to be able to fill in the SleepSure Questionnaire with or without assistance

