# 7. STUDY PROCEDURES

### 7.1. Recruitment

A ward nurse, part of the direct care team on the ward, will approach potential participants on their arrival on the ward, usually as part of the admission assessment process. If they fulfil the inclusion criteria without exclusion characteristics the patient will be given a brief description of the study and a

Clinical Research Protocol Template version 10.0 CONFIDENTIAL © Copyright: The University of Oxford and Oxford University Hospitals NHS Foundation Trust 2015 Page 8 of 15 Patient Information Sheet; with the permission of the patient any relatives present will also have the study explained and will be given a Patient Information Sheet. They will then be approached by the SleepSure research nurse who will consent and register the patient as a participant.

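### Section 10.3 drops participants without a completed sleep form from length of stay, falls and zopiclone, which do not need it; the undefined form timing is one route to such loss

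*Combined protocol and SAP*

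**What the plan says.** **Analysis set.** Section 10.3 uses the data of all participants except those who withdrew consent or left the questionnaire uncompleted. It makes no distinction between outcomes.

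**Sources.** Section 4 takes the primary outcome from the questionnaire. The other clinical outcomes come from routine records after discharge: "Length of stay data from hospital administration system", electronic drug charts for sleep medication, and centrally collated falls data.

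**Timing.** Section 4 has "Questionnaire given >1 day after recruitment", and section 5 has "SleepSure sleep questionnaire will be given to all patients >1 day after recruitment". Sections 6.2, 7.2 and 7.6 use the same time point. None says whether a day means 24 hours or the next calendar day. The only timing exception, in 7.8, is for patients still in hospital when follow-up closes.

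**Eligibility and entry.** Section 3 loosely describes people admitted "onto any ward admitting eligible patients for at least one night". The working criterion, in 6.2, is "Be expected to stay in Oxford University Hospitals NHS Foundation Trust for at least one more night". A ward nurse "will approach potential participants on their arrival on the ward", section 7.3 allows no gap between contact and recruitment, and the envelope is opened at recruitment (7.4).

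**Consent.** Section 7.2 requires written consent, and its verbal explanation covers the routine data on falls, sleeping tablets and stay. It also treats a form that was presented but not filled in as refusal for that data. A note in the capacity criterion of 6.2 adds: "Data will not be collected from individuals who are unable to give consent with the filling in of the SleepSure questionnaire".

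**The concern.** Whether a form is completed is decided after the envelope is opened. It can depend on how soon the patient goes home, and section 10.1 expects the intervention group to go home sooner. Restricting the length-of-stay comparison to completers therefore selects patients partly on the outcome being compared. Falls and zopiclone use are counted over the same stay. The arms being compared are then no longer the randomised arms, although the records for those left out exist.

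The timing rule shows how this could happen without any refusal. A patient recruited at 16:00 and discharged at 11:00 next day satisfies 6.2 but leaves after 19 hours. If the form is due only after 24 hours, that patient is randomised, never offered the form, and then dropped from every outcome by 10.3.

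**Working it through.** **1. The plan's own figure.** The total of 400 cannot be reproduced. Section 10.2 says there are no data for a sample size calculation or on loss of patients, and no effect, SD, alpha or power is given. Everything below rests on assumptions: 200 per arm, two-sided alpha 0.05, 80% power.

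**2. Loss through the timing rule, on the 24-hour reading.** Let q be the share of participants who stay one night and f the fraction of those who leave within 24 hours of recruitment. Loss = q × f. With clock times uniform, f is the probability that discharge falls at an earlier clock time than recruitment:
- recruited 09–13h, discharged 13–18h: f = 0
- recruited 09–13h, discharged 10–17h: f = 0.16
- recruited 12–18h, discharged 10–17h: f = (45/14 + 1)/6 = 0.70

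With q assumed to be 0.10 to 0.25, loss runs from 0 to 0.25 × 0.70 = 17.5%, or 0 to 70 of 400. This is a range of assumptions, not a bound: recruitment at 12–20h with discharge at 09–17h gives f of about 0.80 and a loss of about 20%. On the next-day-or-later reading, loss by this route is about zero.

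**3. Precision.** Detectable difference = (1.960 + 0.842) × √(2 / (200 × (1 − loss))).
- no loss: 0.280 SD
- 10%: 0.295 SD
- 17.5%: 2.802 × √(2/165) = 0.308 SD
- 20%: 0.313 SD

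**4. Unequal loss.** Suppose nights are geometric with mean 4 in control and 3.6 in intervention (a 10% cut), and f = 0.70. Loss is then 0.70/4 = 17.5% against 0.70/3.6 = 19.4%.

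**5. Length of stay among those kept.** In the models counted in nights, each lost patient contributes one night, so the kept mean is (m − fq)/(1 − fq), where m is mean nights. In the geometric model q = 1/m. In the shift model, 5% of intervention patients go home after one night instead of two, so m falls by 0.05 and q rises by 0.05. The lognormal model (log SD 0.8) drops remaining stays of 24 hours or less, by simulation.

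| Stay model | True difference | Difference in those kept |
|---|---|---|
| Geometric, m = 4 against 3.6, f = 0.35 | −0.400 night | −0.408 night |
| Lognormal, median 48 h, 10% cut | −6.6 h | −5.4 h (82%) |
| Lognormal, median 96 h, 10% cut | −13.4 h | −12.4 h (93%) |
| 5% shifted, m = 4, f = 0.16 | −0.05 night | 4.099 − 4.125 = −0.026 night |
| 5% shifted, m = 10, f = 0.70 | −0.05 night | 11.000 − 10.677 = +0.32 night |

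For the last row, control is (10 − 0.07)/0.93 and intervention is (9.95 − 0.105)/0.895.

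**6. Scale.** The detectable difference in mean stay is 0.28 × SD. For the geometric model SD = √(m(m − 1)), giving 0.28 × 3.46 = 0.97 night at m = 4 and 0.28 × 9.49 = 2.7 nights at m = 10. For the lognormal model with median 48 h, the mean is 48 × e^0.32 = 66.1 h and the SD is 66.1 × √(e^0.64 − 1) = 62.6 h, giving 17.5 h. Every shift in the table is well below the corresponding figure.

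These sums cover the timing route only. The documents offer no input for forms missed through refusal, loss of capacity or a missed nurse visit, and 10.3 treats all of these the same way.

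**The case against.** The best defence concerns timing. Section 5 promises the form to all patients, and 6.2 asks for likely capacity at the moment of filling it in. Both presuppose that the patient is still there, which fits a reading of next day or later, and on that reading the timing loss nearly vanishes. This stands: the timing rule is mainly a definition to settle. It does not rescue 10.3, which excludes non-completers whatever the cause.

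A reader might infer that the plan must lose its one-night patients, or that eligibility and timing flatly contradict each other. The documents do not support that, because the conflict arises only on the 24-hour reading and then only for patients who leave within 24 hours.

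A reader might also infer that the consent wording already bars the routine data. The note in 6.2 concerns people unable to consent, not people who have gone home. The refusal rule in 7.2 reaches only patients who were presented with the form, and it can be read as limited to the form's own data. Neither clearly requires the exclusion in 10.3, although both need tidying if 10.3 changes.

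Finally, the calculated effects are small. That is correct for the timing route, and it limits how much weight the point carries.

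**Conclusion.** The point holds for the analysis set. Section 10.3 makes three routine-record comparisons conditional on a post-randomisation event that those outcomes do not need, and nothing is gained by it.

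The timing part holds conditionally. On the 24-hour reading, with assumed one-night shares of 10% to 25% and 0% to 70% of those leaving within 24 hours, loss is 0% to 17.5% and the detectable effect is at most 0.31 SD instead of 0.28. On the other reading, loss is about zero.

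It would be tempting to say that length of stay will be biased in a known direction, or that its sign will reverse. The documents do not support either. The error is close to nil, an attenuation or a reversal depending on the stay model, and the reversal shown starts from a true effect of only 0.05 night. In the models tried, the shift is below what 400 patients could detect. The change is worth making because it is cheap and restores a randomised comparison, not because a large error has been shown.

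**What to change.** 1. **Amend 10.3**, for example: *Length of stay, falls and zopiclone are analysed for all randomised participants who have not withdrawn consent, in the arm allocated, whether or not a questionnaire was completed. The sleep score uses all completed questionnaires.* Limit the refusal rule in 7.2 to questionnaire data. State in 6.2 that the note does not bar routine data from participants who gave written consent at recruitment.
2. **Define the time point once**, and use it in sections 4, 5, 6.2, 7.2 and 7.6. It should be one that every eligible patient can reach and the same in both arms, for example the morning after the first night following randomisation and before discharge. A next-morning fallback should not be added: a one-night patient has gone home by then, and it would mix first-night with second-night scores.
3. **Record the recruitment date and the form completion date**, neither of which is among the fields listed in 7.6. Report missing forms with reasons by arm.

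The cost is a protocol amendment with ethics approval, matching consent wording, two date fields and a nurse round before discharge. The routine records are already in the plan. The scientific downside is that an early measure captures less adaptation to the earplugs and mask. The change is best made before the pilot, because section 5 says: "If no changes to the protocol are made then this pilot data will be incorporated with the data proper".
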